5.5 PHARMACOKINETIC POPULATION

The Pharmacokinetic Population is defined as all subjects in the Safety Population with at least one evaluable plasma concentration of escitalopram or S-demethylcitalopram.

Page 17 of 53

6.0 SUBJECT DISPOSITION

The number of subjects in 3 of the study populations (Randomized, Safety, and mITT) will be summarized by treatment group and study center; the Screened Population will be summarized overall only by study center.

Screen-failure subjects (i.e., subjects screened but not randomized) and the associated reasons for failure to randomize will be tabulated overall for the Screened Population. Subjects who are randomized but not in the Safety Population will be listed.

Subjects completing the Week 8 assessment of double-blind acute treatment period will be considered completers. The number and percentage of subjects who complete the double-blind acute treatment period and of subjects who prematurely discontinue during the same period will be presented for each treatment group and overall for the Safety Population.

The reasons for premature discontinuation from the double-blind acute treatment period as recorded on the disposition pages of the electronic case report forms will be summarized (number and percentage) by treatment group for the Safety Population. All subjects who prematurely discontinue during the double-blind acute treatment period will be listed by discontinuation reason for the Safety Population.

The number and percentage of subjects impacted by the COVID-19 pandemic will be summarized by treatment group and overall for the Screened Population. The summary will also include the extent of the impact, including:

- discontinuations related to COVID-19 during screening, double-blind acute treatment period, and down-taper period
- visits missed due to COVID-19
- video/phone visits conducted in place of on-site visits due to COVID-19
- assessments missed due to COVID-19 (this will only include assessments missed that were not permitted to be missed during off-site visits)
- significant protocol deviations related to COVID-19
- study drug disruption due to COVID-19
- TEAEs of coronavirus infection or positive coronavirus test

The number and percentage of subjects with missing or remote visits and with missing assessments due to COVID-19 will be summarized by treatment group and overall for each visit:

Page 18 of 53

The number and percentage of subjects with significant protocol deviations will be summarized overall and by treatment group for the Randomized Population. Deviations related to the following categories will be included:

- inclusion or exclusion criteria
- withdrawal criteria
- treatment or dose
- concomitant medications

These and any additional significant protocol deviations will be reviewed and documented before database lock and unblinding of treatment codes.

Significant protocol deviations that occur due to COVID-19 will be summarized separately. All protocol deviations that occur due to COVID-19 will be listed.

Page 19 of 53

7.0 DEMOGRAPHICS AND OTHER BASELINE CHARACTERISTICS

7.1 DEMOGRAPHICS

Demographic parameters (age, age group [7-11 vs. 12-17 years], sex, race, ethnicity, weight, height, BMI, BMI z-score group [≥ 2 , < 2]) and other baseline characteristics will be summarized descriptively by treatment group and overall for the Safety and mITT populations, respectively.

Continuous variables will be summarized by number of subjects and mean, SD, median, minimum, and maximum values. Categorical variables will be summarized by number and percentage of subjects.

7.2 MEDICAL HISTORY

Medical history will be classified by system organ class and preferred term using the Medical Dictionary for Regulatory Activities (MedDRA), version 22.0 or newer. The number and percentage of subjects in each system organ class (SOC) and preferred term (PT) will be summarized by treatment group for the Safety Population.

Psychiatric history and result from MINI Kid will also be summarized descriptively by treatment group for the Safety Population.

Listings of medical history, psychiatric history and results from MINI Kid will be presented

7.3 CONCOMITANT MEDICATION

The World Health Organization Drug Dictionary, version Global B3, Mar 2019 or newer, will be used to classify prior and concomitant medications by therapeutic class and drug name.

Prior medication is defined as any recorded medication taken before the date of the first dose of double-blind investigational product. Concomitant medication is defined as any medication taken on or after the date of the first dose of double-blind investigational product through the last study visit, including the follow-up call. The imputation of incomplete and missing start/stop date of medication are specified in the section 17.

Both prior and concomitant medications use will be coded by PT and Anatomic Therapeutic Class 4 (ATC4). The use of prior and concomitant medications will be summarized by the number and percentage of subjects in each treatment group and overall for the Safety Population. Summaries will be ordered in alphabetical order of ATC4 and then, within an ATC4, in decreasing frequencies by PT in total column. If a

Page 20 of 53

subject took a specific medication multiple times or took multiple medications within a specific therapeutic class, that subject would be counted only once for the coded drug name or therapeutic class.

Summaries for concomitant medication use will be presented for the double-blind acute treatment period and the down-taper period, separately. Any concomitant medications which started after the date of the last dose of double-blind investigational product in the study will not be presented in the summary tables but will be included in the subject data listings.

Page 21 of 53

8.0 EXTENT OF EXPOSURE AND TREATMENT COMPLIANCE

8.1 EXTENT OF EXPOSURE

Total exposure to double-blind investigational product for the Safety Population during the double-blind acute treatment period will be summarized, calculated as the number of days from the date of the first dose of double-blind investigational product taken to the date of the last dose taken through the Week 8 End of Treatment or Early Withdrawal visit, inclusive. Descriptive statistics (n, mean, standard deviation, minimum, median, and maximum) will be presented by treatment group. Similarly, the treatment duration in the down taper period, defined as the first dose in the down taper period to the last dose in the down taper period, inclusive, will be summarized. The total duration of double-blind investigational product exposure, defined as the sum of the treatment duration through Week 8 and the duration in the down taper period will be summarized.

The number and percentage of subjects who had their dosage escalated at Week 2 from 10 mg/day to 20 mg/day will be summarized by treatment group. The denominator will be the number of subjects who had study medication dispensed at Week 2. Similarly, the number and percentage of subjects who had their dosage escalated at Week 4 from 10 mg/day to 20 mg/day will be summarized by treatment group. The number of subjects who required a dose reduction from 20 mg/day to 10 mg/day will be summarized by treatment group. The number of days from first date of escalation to 20 mg/day to the dose reduction will be summarized using descriptive statistics.

The mean daily dose of investigational product between visits and overall during doubleblinded acute treatment period will be summarized by treatment group for the Safety Population. The calculation is as below:

Mean daily dose = (Total dose taken during the interval) / (Total number of days in the interval).

Total number of days = Stop date of study drug - start date of study drug + 1.

The total dose, start date, and stop date will be based on the eCRF Study Drug Administration page.

8.2 MEASUREMENT OF TREATMENT COMPLIANCE

Dosing compliance for a specified period is defined as the total number of capsules actually taken by a subject during that period divided by the number of capsules prescribed to be taken for the same period multiplied by 100. The total number of capsules actually taken during a specific time period is calculated based on the study medication record. The number of capsules prescribed to be taken for a specific treatment period will be calculated by multiplying the number of days in that period by the number of capsules to be taken per day.

Page 22 of 53

Descriptive statistics for investigational product compliance will be presented by treatment group for each period between 2 consecutive visits, as well as for the entire double-blind acute treatment period, the period from first dose to the Week 8 End of Treatment or Early Withdrawal visit, and the down taper period.

Page 23 of 53

9.0 EFFICACY ANALYSES

The efficacy analyses will be based on the mITT Population. Baseline for efficacy is defined as the last non-missing efficacy assessment before the first dose of double-blind investigational product. All statistical tests will be 2-sided hypothesis tests performed at the 5% level of significance for main effects. All confidence intervals will be 2-sided 95% confidence intervals, unless stated otherwise.

For efficacy analyses in which study center is a factor, a small center will be defined as a center with fewer than 2 subjects in any treatment group in the mITT Population. Small centers will be pooled to form pseudo-centers so that each treatment group includes at least 2 mITT subjects within the center. Pooling will be done (within each country first) using the following algorithm:

Based on the number of mITT subjects, small centers will be ordered from the largest to the smallest, and centers of the same size will be ordered from the largest center code to the smallest center code. The pooling process starts with the largest small center from the top, which will be pooled with the smallest from the bottom until a non-small pseudo center is formed. The process will be repeated using the small centers left out after the first pass. If any centers are left out at the end of the process, they will be pooled with the smallest pseudo center. If there is more than 1 smallest pseudo center, the pseudo center with the smallest center code will be selected. In case that the pseudo center formed by pooling all small centers is still a small center, it will be pooled with the smallest non-small center. If there is more than 1 smallest non-small center, the one with the smallest center code will be selected.

These pseudo-centers will be used for all efficacy analyses when the model is adjusted for study center.

By-visit analyses based on the mixed-effects model for repeated measures (MMRM) using the observed case (OC) approach will be performed for all continuous efficacy parameters with multiple post-baseline measurements.

9.1 PRIMARY EFFICACY PARAMETER

9.1.1 Primary Objective Estimand

The estimand used to address the primary objective "To determine efficacy of escitalopram relative to placebo in the acute treatment of children (aged 7 through 11 years) and adolescents (aged 12 through 17 years) who meet criteria for GAD as defined in the Diagnostic and Statistical Manual of Mental Disorders" is defined by the following:

• Population:

Page 24 of 53

- The target population is children (aged 7 through 11 years) and adolescents (aged 12 through 17 years) with GAD and who satisfy the inclusion and exclusion criteria as specified in the protocol.
- The analysis population is mITT population defined in section 5.4.

Variable:

O Change from baseline to Week 8 in PARS severity. The PARS severity score is derived by summing 5 of 7 severity/impairment/interference items (2, 3, 5, 6, and 7).

Intercurrent events:

- To evaluate the efficacy at Week 8 in the mITT population, participants are assumed to adhere to the assigned treatment for the duration of the study. As a result, data after the discontinuation from the study treatment due to all reasons will not be included in the primary analysis and they will be assumed as missing at random.
- For the sensitivity analyses of primary parameter, the LOCF approach and pattern-mixture model approach will be utilized to impute the missing value. The details are provided in Section 10.1.2.
- Population-level summary:
 - The change from baseline of PARS severity score at Week 8 in subjects treated with escitalopram compared to the change from baseline of PARS severity score at Week 8 in subjects treated with placebo

9.1.2 Analysis of Primary Parameter

The primary efficacy parameter is the change from baseline to Week 8 in PARS severity. The PARS severity score for GAD is assessed for all symptoms identified in the generalized anxiety section of the PARS symptom checklist. The PARS severity score for GAD will be derived by summing 5 of 7 severity/impairment/interference items (2, 3, 5, 6, and 7). If any of the items is missing, the severity score will be considered missing.

The primary analysis will be performed using an MMRM with treatment group, age group strata (7-11 vs. 12-17 years), sex, pooled study center, visit, and treatment group-by-visit interaction as the fixed effects and the baseline value and baseline value-by-visit interaction as the covariates. An unstructured covariance matrix will be used to model the covariance of within-subject scores. The Kenward-Roger approximation (Kenward and Roger, 1997) will be used to estimate denominator degrees of freedom. If the model convergence for the unstructured covariance matrix fails, then the Fisher scoring

Page 25 of 53

algorithm will be used to provide better initial values of the covariance parameters. In the event that the model still does not converge after using those initial values, simplified covariance structures will be used to fit the model in the following order until the model converges: (1) ante-dependence, (2) heterogeneous autoregressive, (3) Toeplitz, and (4) compound symmetry. If a structured covariance is used, then a robust sandwich estimator will be used for estimating the variance of the treatment effect estimate.

This analysis will only use the observed cases of post-baseline scores without imputation of missing values. The significance test for the difference in means at Week 8 will be based on least squares (LS) means using a 2-sided α of 0.05. Differences between treatments at the other post-baseline visits will also be estimated based on LS means.

The primary analysis will treat measurements after study withdrawal as missing in the MMRM modeling, leading to an estimate of the treatment effect while on treatment. Two sensitivity analyses, last observation carried forward (LOCF) and pattern-mixture model, will be performed on the primary efficacy parameter to assess the impact of the missing at random assumption of MMRM.

For the LOCF approach, only the postbaseline PARS severity score for GAD will be imputed; individual item scores will not be carried forward to derive the PARS severity score. Baseline total score will be carried forward only for the missing scores immediately after baseline. If all the postbaseline values are missing, the baseline value will not be carried forward. The LOCF approach is based on an analysis-of-covariance (ANCOVA) model including treatment group and pooled study center as factors and baseline PARS severity score as a covariate

Another sensitivity analysis using a pattern-mixture model approach based on non-future dependent missing value restrictions (Kenward et al., 2003) will be performed to assess the robustness of the primary MMRM results to the possible violation of the missing-at-random assumption. The details of this sensitivity analysis are as follows:

The pattern for the pattern-mixture model will be defined by the subject's last visit with an observed value. The observed PARS severity score at a visit is assumed to have a linear relationship with the subject's prior measurements. The missing values will be imputed under the assumption that the distribution of the missing observations differs from that of the observed only by a shift parameter value Δ . The dataset with missing values imputed will be analyzed using an analysis of covariance (ANCOVA) model with treatment group and pooled study center as factors and baseline PARS severity score as a covariate for between–treatment group comparisons at Week 8. The imputation of missing values and the analysis will be performed multiple times and the inference of this sensitivity analysis will be based on the combined estimates using the standard multiple imputation technique. The shift parameter values Δ for the multiple imputation will start at 0 and increase by 1 to 6 or until a tipping point is reached (ie, the p-value switches from ≤ 0.05 to ≥ 0.05), whichever is higher.

Page 26 of 53

More details of the proposed pattern-mixture model approach (e.g., the models for the pattern-specific identifiable densities and the unidentified conditional distributions, the shift parameter Δ , and the multiple imputation algorithm) are provided in Appendix I to this SAP.

To examine the consistency of the primary efficacy results across study centers, the treatment differences versus placebo treatment groups (mean \pm SE) in the change from baseline to Week 8 in PARS severity score, both OC and LOCF, will be graphed by pooled study center.

The comparison of escitalopram vs. placebo will be performed to assess study assay sensitivity.

To assess the impact of COVID-19 on the primary efficacy parameter:

- The primary analysis will be repeated for subjects that were not significantly impacted by COVID-19 (Global COVID-19 Impact Assessment score of 4 or higher, regardless of direction of impact; see section 9.2.5).
- A sensitivity analysis will be conducted by treating remote visits as missing, and analyzing the remaining data using the primary MMRM model.
- A sensitivity analysis will be conducted by repeating the primary analysis and adding the following to the model: an indicator of whether data was collected before or on and after the start of the pandemic (17 March 2020) and the indicator by treatment interaction.
- A subgroup analysis will be conducted by repeating the primary analysis for randomized patients before or on and after the start of the COVID-19 pandemic (17 March 2020).

The subject-level PARS scores will be listed

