8.4.4 Method of Assigning Subjects to Treatment Groups

After successfully meeting study entry criteria, subjects will be randomized in a 1:1 ratio to escitalopram or placebo. The randomization schedule will be stratified by age at randomization (grouped as 7–11 years vs. 12–17 years) and sex, and blocked.

Approximately 430 subjects will be screened and a total of approximately 256 subjects are planned for randomization.

An Interactive Response System (IXRS) will be used to manage the randomization, assignment of treatment during the study, and if necessary emergency unblinding of subjects during the study conduct. The IXRS will assign a randomization number, distinct from the subject number, at the time of randomization.

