Note that the two distributions only differ by a shift (Δ) parameter. When $\Delta = 0$, the missing value y_s in Pattern s-l is imputed based on the distribution of all observed data up to Visit s, as a result, leading to missing at random (MAR) missingness. When $\Delta \neq 0$, (8) will introduce a scenario of MNAR. The similar idea was also presented in the recent publication "The Prevention and Treatment of Missing Data in Clinical Trials" by the National Academies Press. The selection of the plausible values for the shift parameter (Δ) is discussed in Section 3 of this appendix.

Note that per recommendation in Wang and Daniels (2011), only the observed data within pattern is assumed to be multivariate normal. The observed data distribution can be expressed in terms of the marginal distribution of baseline measurement and the conditional distributions of postbaseline measurements given earlier measurements. Assuming that these distributions are normal, the linear regression of each observation on prior observations will yield least-squares estimates of model parameters that can be utilized for independent posterior draws of model parameters for observed data. Multiple imputation approach will be used to estimate the overall mean at the final time point.

Page 55 of 53

2. Imputation Procedure

All the missing data will be imputed to create complete datasets, then statistical analysis can be performed using appropriate techniques such as ANCOVA. The imputation can accommodate MNAR missing data mechanisms, based on the theory discussed in the previous section.

The model parameters for each dropout pattern, i.e., the mean, variance and proportions of observations in each pattern, are drawn from their posterior distributions prior to the imputation of missing data for a single imputation.

The details of imputation within a pattern, say Pattern t, are as the following:

Step 1. Impute the first missing value v_{t+1} for each subject in Pattern t (t = 1, ..., T-1):

- a. Compute estimates of mixture probabilities $\lambda_{s-l,j}$ in (7) with s = t+1 given the posterior draw of proportions of observations in each pattern and the posterior draw of regression parameters for the observed data.

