- b. Draw a random integer from $\{s, ...T\}$ to index a component distribution on the right hand side of (6), using mixture probabilities obtained in a). Draw y_{t+1}^* from the identified component normal distribution. Impute the missing y_{t+1} as $\widetilde{y}_{t+1} = y_{t+1}^* + \Delta$.

Step 2. Impute the rest of the missing values of $y_{t+2}, y_{t+3}, ..., y_T$ for subjects in Pattern t:

Starting with imputation for y_{t+2} , first, similar to Step 1, draw y_{t+2}^* from the normal mixture (6) based on the observed $y_1,...,y_t$ and the already imputed \tilde{y}_{t+1} for the subject.

Then the missing y_{t+2} is imputed as $\widetilde{y}_{t+2} = y_{t+2}^* + \Delta$ with probability δ_{t+1} and as $\widetilde{y}_{t+2} = y_{t+2}^*$ with probability $I - \delta_{t+1}$, where the mixture probability $\delta_{t+1} = \omega_{t+1,t+1}$ is obtained from (4) given the posterior draw of proportions of observations in each pattern and the posterior draw of regression parameters for the observed data.

Missing values of y_{t+3} through y_T can be imputed similarly as y_{t+2} .

To summarize, the imputations of y_{t+1} through y_T is done recursively within each Pattern t (for all t = 1,..., T - 1) to create a complete dataset after imputation is done for all patterns with missing values.

Page 56 of 53

The above imputation procedure is applied to all subjects in each missing data pattern to create a single imputed data set. Repeating the process of drawing parameters from the posterior distribution and imputing missing data given the posterior draw m times will yield m imputed data sets. The observed or imputed values at the final data point are averaged to obtain the overall mean estimate for each imputed data set, and the multiple imputation estimate is obtained by averaging the estimates across m imputations.

In this sensitivity analysis, m is set to equal to 20. The value of m is discussed in the context of imputation efficiency in standard multiple imputation theory (Rubin, 1987, p. 114), and m = 20 would provide at least 96% of relative efficiency as compared with using an large number of imputations (SAS/STAT User's Guide, p. 3796).

3. Determination of the Shift Parameter Values

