The common shift parameter Δ is the difference between the mean of y_{t+1} among those who drop out at Visit t and those who remain beyond Visit t ($1 \le t \le T - 1$). The exact value of Δ is unknown and can't be estimated from data because of missingness. The magnitude of Δ depends on the medical aspects of the trial. Using relevant historical data, one may select Δ as a proportion of the sample standard deviation or a proportion of observed treatment efficacy.

References:

Rubin DB. Multiple Imputation for Nonresponse in Surveys. J. Wiley & Sons, New York; 1987.

SAS Institute Inc. SAS/STAT 9.2 User's Guide, Second Edition. Cary, NC: SAS Institute Inc; 2009.

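### The LOCF and pattern-mixture ANCOVAs leave out age group and sex, which stratify randomization and are in the primary MMRM

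*SAP*

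**What the plan says.** - **Randomization.** Protocol 8.4.4 says the schedule "will be stratified by age at randomization" (7–11 vs. 12–17 years) and also by sex.
- **Primary analysis.** SAP 9.1.2 fits an MMRM with treatment group, "age group strata (7-11 vs. 12-17 years), sex, pooled study center, visit, and treatment group-by-visit interaction as the fixed effects", plus baseline and baseline-by-visit as covariates.
- **Purpose of the checks.** The same section adds LOCF and a pattern-mixture model "to assess the impact of the missing at random assumption of MMRM".
- **LOCF.** An ANCOVA "including treatment group and pooled study center as factors and baseline PARS severity score as a covariate".
- **Pattern-mixture.** Multiple imputation, then an ANCOVA "model with treatment group and pooled study center as factors and baseline PARS severity score as a covariate".
- **Zero shift.** SAP Appendix I describes a shift of zero as "leading to missing at random (MAR) missingness", so that run is the natural one to compare with the MMRM.

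Protocol 11.5.1.1 and 11.5.1.1.1 leave the details of the sensitivity analyses to the SAP. The SAP does not explain the shorter covariate list.

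**The concern.** A check on a missing-data assumption is easiest to read when only that assumption changes. Here two design factors drop out as well. Stratified, blocked randomization balances the arms on age group and sex, so omitting them should not bias the treatment estimate on average. But if they are prognostic, their variance stays in the residual, and the reported standard error overstates the true uncertainty.

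The two checks, including the zero-shift run, can therefore differ from the primary result partly because of covariates. Most often this makes the result look less robust than it is. It matters only when the result is borderline. Movement from shift 0 to larger shifts is not affected, because every shift uses the same ANCOVA.

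Saving degrees of freedom is not an obvious reason for the omission. Both ANCOVAs keep pooled study center, which has many levels, and drop two one-degree-of-freedom factors.

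**Working it through.** **Inputs from the documents.** Difference 2.30, SD 5.79, 128 per arm, correlation 0.7, dropout 14%, power 85% (SAP 14.0; Protocol 11.9). PARS after baseline at Weeks 2 and 8 (SAP 3.2). About 40 centers (Protocol 8.3.1), pooled by the SAP 9.0 algorithm. 20 imputations (SAP Appendix I).

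**The plan's own figure.** The effect size is 2.30 / 5.79 = 0.397 (stated as 0.39). With two visits and retention r₁ and r₂, the variance factor for the Week 8 mean is (1 − ρ²)/r₂ + ρ²/r₁. Assuming r₁ = 0.93 and r₂ = 0.86, this is 0.51/0.86 + 0.49/0.93 = 1.120. The effective n is 128 / 1.120 = 114 per arm. Power = Φ(0.397 / √(2/114.3) − 1.96) = Φ(1.04) = 85.2%. Other dropout and visit patterns give 114 to 120 per arm and up to 86.8%. The stated 85% is reproduced and does not depend on this point.

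**Expected size.** Let R² be the share of outcome variance that age group and sex explain beyond the other terms. The documents do not give it, so 0, 0.02, 0.05 and 0.10 are assumed. Omitting the factors inflates the standard error by about 1/√(1 − R²) = 1.000, 1.010, 1.026, 1.054.

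**Simulation A: 3,000 trials per setting, true effect −2.30.** Further assumptions: blocks of 4, four equal strata, uneven center sizes (mean 27.6 pooled centers), dropout at random, Week 2 effect half of Week 8, strata effects equal at both visits, imputation by arm.

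| Assumed R² | 0 | 0.02 | 0.05 | 0.10 |
|---|---|---|---|---|
| LOCF SE, without / with strata | 0.758 / 0.759 | 0.759 / 0.752 | 0.761 / 0.742 | 0.759 / 0.721 |
| LOCF SE excess (from unrounded SEs) | 0% | 1.0% | 2.6% | 5.4% |
| Shift-0 SE, without / with | 0.792 / 0.792 | 0.792 / 0.786 | 0.793 / 0.777 | 0.790 / 0.756 |
| Shift-0 SE excess | 0% | 0.8% | 2.1% | 4.5% |
| LOCF significant only with strata | 0.37% | 1.07% | 1.77% | 2.90% |
| LOCF significant only without | 0.30% | 0.30% | 0.27% | 0.30% |
| Shift 0 significant only with strata | 0.27% | 0.80% | 1.37% | 2.07% |
| Shift 0 significant only without | 0.23% | 0.40% | 0.47% | 0.20% |

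Adding each pair of rows, the verdict changes in 0.7 / 1.4 / 2.0 / 3.2% of trials for LOCF and 0.5 / 1.2 / 1.8 / 2.3% for shift 0. Mean estimates with and without strata agree within 0.003. Under the null, LOCF rejects in 4.6 / 4.8 / 4.0 / 3.8% of trials without strata and 4.7 / 4.9 / 4.6 / 5.1% with. A simpler simulation (4,000 trials per setting, no center or baseline term) also gave a 0 to 5% SE excess.

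**Simulation B: 2,500 trials per setting, true effect −2.30, with the primary MMRM also fitted.**

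| Assumed R² | 0 | 0.02 | 0.05 | 0.10 |
|---|---|---|---|---|
| LOCF verdict differs from MMRM, without / with | 5.3 / 5.2% | 5.0 / 4.6% | 6.1 / 4.8% | 6.2 / 4.0% |
| Shift-0 verdict differs from MMRM, without / with | 3.4 / 3.2% | 3.2 / 3.1% | 3.6 / 3.0% | 4.2 / 2.8% |
| Borderline MMRM: LOCF loses significance, without / with | 22 / 22% | 22 / 20% | 29 / 22% | 33 / 19% |
| Borderline MMRM: shift 0 loses significance, without / with | 12 / 11% | 12 / 11% | 15 / 10% | 21 / 11% |

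Borderline means a primary p between 0.01 and 0.05, which occurred in 18–21% of trials.

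**Tipping point.** Appendix I refers to "The common shift parameter" and imputes in both arms: "The above imputation procedure is applied to all subjects in each missing data pattern to create a single imputed data set". With the same shift in each arm, the median tipping shift is 22–23 without strata and 23–24 with. Both lie far beyond the prespecified range of 0 to 6, so the omission is unimportant there at the planned effect.

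**The case against.** The strongest reply is that this hardly matters. There is no average bias, the tests are conservative if anything, and the direction that could flatter the drug (significant only without strata) occurs in 0.2–0.5% of trials. That is correct, and it is why the point is minor.

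Four further points qualify the figures:

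- **R² is assumed.** Nothing in the documents shows that age group or sex predicts PARS change. Even at R² = 0, adding two irrelevant factors changes 0.7% (LOCF) and 0.5% (shift 0) of verdicts, so part of the later percentages is background. The 33% vs. 19% contrast needs the highest assumed R² and a borderline primary result.
- **Most of the gap to the MMRM remains after the change.** At R² = 0.10, disagreement falls only from 6.2 to 4.0% for LOCF and from 4.2 to 2.8% for shift 0.
- **The imputation step differs too.** It regresses on prior scores only (SAP 9.1.2 and Appendix I), so shift 0 would still condition on fewer variables than the MMRM.
- **Early-withdrawal visits.** Simulation B uses Weeks 2 and 8 only. PARS is also taken at early withdrawal, and the SAP 16.1 windows can place that score at Week 4 or 6. The comparisons with the MMRM are therefore illustrative. The SE ratio should be largely unaffected.

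It is also true that neither document promises identical covariates and that the ANCOVAs are fully prespecified. That rules out a charge of analyst discretion, but it gives no reason to drop the design factors.

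**Conclusion.** The point holds and is minor. Both sensitivity ANCOVAs omit the two stratification factors that the primary model includes, without explanation. Over an assumed R² of 0 to 0.10, the reported standard error is too large by 0 to 5.4% (LOCF) and 0 to 4.5% (shift 0). This makes the checks slightly conservative and can matter for a borderline result. If the factors are not prognostic, the effect is close to zero. The omission from the text is certain. The size rests on the assumed R² and the simulation settings. The primary analysis, its type I error, the sample size and the power are not touched.

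**What to change.** In SAP 9.1.2, add age group (7–11 vs. 12–17 years) and sex as factors to the LOCF ANCOVA and the pattern-mixture ANCOVA, or state why they are left out. This removes one avoidable difference from the MMRM but does not make the models identical. If closer agreement at shift 0 is wanted, the sponsor could also consider the two factors in the imputation regressions, or note that these use prior scores only. The main change costs SAP wording and two error degrees of freedom in each ANCOVA. Data collection, the primary analysis and the imputation step stay as they are.
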